1.5 Benefit/risk and ethical assessment

1.5.1 Potential risks

The important potential risks, based on the mechanism of action of Durvalumab and reported toxicities include immune-mediated reactions such as enterocolitis, dermatitis, hepatitis/hepatotoxicity, endocrinopathy, pneumonitis, nephritis, pancreatitis (elevated amylase/lipase), and neuropathy or neurologic events. Additional important potential risks include infusion-related reactions, hypersensitivity, and anaphylaxis or serious allergic reactions. Other potential/theoretical risks include serious infections and immune complex disease. The most common treatment-related toxicities included fatigue, nausea, and diarrhea with <1% of cases of colitis or pneumonitis.

Adverse events resulted in the discontinuation of treatment in 10.8% of patients, were serious in 30.6%, and were Grade \geq 3 in 34.3% of patients treated with Durvalumab monotherapy.

Recent data are available for patients with SCCHN in the expansion cohort of a PhaseI/II ongoing study (Segal et al 2015).Drug-related AEs were observed in 60% of pts; the most frequent were fatigue (11%), diarrhea, (8%), and nausea (7%). Grade \geq 3 related AEs were reported in 7% of pts: rash (2 pts), and increased GGT, fatigue, and tumor inflammation (1 pt each). No drug-related AEs led to discontinuation or death. No colitis or grade \geq 3 pneumonitis was observed.

1.5.2 Potential benefits

Patients are being enrolled in 5 ongoing clinical studies of Durvalumab as monotherapy in patients with SCCHN. No studies have yet been completed. An ongoing phase I/II, multicenter, open-label study (NCT01693562) is evaluating the safety and efficacy of Durvalumab in multiple solid tumor types including SCCHN (Segal et al 2015). Sixty-two SCCHN patients were treated with Durvalumab as monotherapy at 10 mg/kg q2w and evaluable for disease assessments as of the data cut-off date of 7 April 2015. Tissue samples were retrospectively tested for PD-L1 expression using an immunohistochemistry (IHC) assay using the Ventana SP263 clone. Of 62 SCCHN patients, an ORR of 11% was observed in the PD-L1-unselected population and in 18% and 8% of patients with PD-L1-positive (n=22) and PD-L1-negative disease (n=37), respectively, with DCR at 24 weeks achieved in 18% and 11% of patients with PD-L1-positive and –negative disease, respectively. DoRs ranged from 41 to 53 weeks in patients with PD-L1 positive disease and 16 to 54 weeks in patients with PD-L1-negative disease, with responses noted in both HPV-positive and -negative patients and in smokers and non-smokers.

1.5.3 Overall benefit/risk and ethical assessment

Durvalumab has demonstrated expected clinical activity and durable response in heavily pretreated patients. Advancing research for use of Durvalumab in earlier treatment stages represents the next step in exploiting this immunotherapeutic agent.

Little is known about effect of Durvalumab on previously untreated tumors, specifically HNSCC.

HPV+ patients, have better prognosis and response to treatment, however they currently undergo the same aggressive and highly toxic regimens as the HPV- patients. There remains a significant unmet medical need for additional, less toxic treatment options for these patients. Preliminary studies show increased presence of immune effector cells in the HPV+ tumor, potentially indicative of increased susceptibility to immunotherapeutic agents such as Durvalumab.

Our study addresses fundamental mechanistic questions about the tumor effect of Durvalumab in previously untreated patients with HNSCC and addresses the potential difference between HPV + and HPV- tumor response. The study designs takes advantage of the window of opportunity for first line drug treatment between the time of diagnosis and time of surgery in patients with SCCHN scheduled for primary surgical resection.

We recognize the importance of safety trial design in this patient population with potential curable disease. The study design aims to minimize potential risks, with intensive, weekly monitoring and safety assessments. The second administration of Durvalumab will be considered prudently with consideration for upcoming surgery. It is recognized, however, that few side-effects are expected with such a short course of treatment.

The overall benefit/risk assessment supports the proposed study design.

2. STUDY OBJECTIVES

2.1 **Primary objectives**

- 2.1.1 The primary objective of this study is to investigate the effect of Durvalumab on local and systemic immune activation by HPV status in patients with oral cavity and oropharynx HNSCC. This will be done by:
 - a) Examining the effects of Durvalumab on systemic immune response to HPV and tumor associated antigens
 - b) Examining the effects of Durvalumab on immune regulatory mechanisms.
 - c) Exploring the association between levels of immune-regulatory miR in plasma and saliva and immune response.

Results will be compared between HPV positive and negative patients to identify a possible differential effect of treatment with Durvalumab. Level of local immune response in the primary tumor and in the regional lymph nodes will be compared whenever possible.

2.2 Secondary objective(s)

- 2.2.1 Investigate the effect of the treatment with Durvalumab on the CT scan and PET scan response.
- 2.2.2 Evaluate the safety of a short induction treatment with Durvalumab.

3. STUDY DESIGN

3.1 Overview of study design

This is a non-randomized, open label, uncontrolled, single group assignment study, to evaluate the anti-tumor effect of Durvalumab in patients with HNSCC when given as a short treatment course before surgery.

A schematic diagram of the overall study design is shown below.

Patients must be scheduled for surgery and have a window of at least 3 weeks between the time of diagnosis and time of surgery.

In order to be eligible for this clinical study, the patients must have fresh tumor tissue frozen and saved in our Tumor Tissue Bank or need to consent for an additional biopsy procedure to obtain a tumor tissue sample for the clinical protocol that will be saved in our Tumor Tissue Bank for the correlative studies. Patients will undergo an assessment on their tumor tissue sample to determine HPV status.

10 HPV+ and 10 HPV- patients will be initially enrolled and need to complete the study. If any patient does not complete the study treatment and investigations, the patient will be replaced.

First administration of Durvalumab will be given with the first visit after registration with the clinical study. Second administration of Durvalumab will be given 2 weeks later. An interval of 3 to 17 days must be ensured for all patients between the last administration of drug and surgery. A 7-14 days interval will be strongly considered and attempted in each case. In the rare circumstances in which surgery was scheduled or delayed at more than 2 weeks after second administration of Durvalumab, a third administration of drug must be given in order to ensure the proposed interval between the last dose of Durvalumab and surgery.

After surgery the patients may proceed with adjuvant treatment as indicated by the stage of their disease and by the surgical pathology findings. A Radiation Oncologist is included in the study team in order to address and to include in the therapeutic algorithm the impact of the potential cytoreduction by Durvalumab therapy on the final surgical and pathologic staging.

Study ends for each patients with the last visit before surgery. However follow up visits will be scheduled monthly after surgery whenever possible and laboratory tests and clinical data will be collected to assess for any adverse events. Subjects who decline to return to the site for evaluations will be offered follow-up by phone up to 3 months as an alternative and the PI will make every effort to collect toxicity data from medical records.

The primary goal of this pilot study is to make use of biopsy tissue obtained before treatment and of the surgical tissue specimen obtained after treatment with durvalumab, in order to assess tissue biomarkers.

Saliva and blood will be collected before each treatment, one week after the treatment and before surgery, and will be analyzed in the same time with tumor tissue.

CT scan or MRI and whenever possible PET scan will be performed before treatment with Durvalumab and before surgery.

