Results will be compared between HPV positive and negative patients to identify a possible differential effect of treatment with Durvalumab. Level of local immune response in the primary tumor and in the regional lymph nodes will be compared whenever possible.

Secondary Objectives:

Investigate the effect of the treatment with Durvalumab on the CT scan and PET scan response.

Evaluate the safety of a short induction treatment with Durvalumab.

Study Design:

This is a non-randomized, open label, uncontrolled, single group assignment study, to evaluate the antitumor effect of Durvalumab in patients with SCCHN when given in a short treatment course before surgery.

10 HPV positive and 10 HPV negative patients will be enrolled, who have an interval longer then 3 weeks between the time of diagnosis and time of surgery.

Two administrations of Durvalumab will be given with an interval of 3 to 17 days between the last administration of drug and surgery. Patients will then undergo surgery as scheduled. After surgery the patients may proceed with adjuvant treatment as indicated by the stage of their disease and by the surgical pathology findings. A Radiation Oncologist is included in the study team in order to address and to include in the therapeutic algorithm the impact of the potential cytoreduction by Durvalumab therapy on the final surgical and pathologic staging.

The primary goal of this pilot study is to make use of biopsy tissue obtained before treatment and of the surgical tissue specimen obtained after treatment with durvalumab, in order to assess tissue biomarkers. Saliva and blood will be collected before each treatment, one week after the treatment and before surgery, and will be analyzed in the same time with tumor tissue.

CT scan or MRI and whenever possible PET scan will be performed before treatment with Durvalumab and before surgery.

The clinical trial will be considered completed as soon as the last patient has completed his last follow up visit, at 1 month after surgical treatment.

Number of Centers: 1

Number of Subjects:

20 patients, 10 patients with HPV positive and 10 patients with HPV negative.

Study Population:

HNSCC of the oral cavity or oropharynx

Inclusion Criteria:

- Histologically or cytologically confirmed SCCHN of the oral cavity (OC; more than 90% patients have HPV negative cancer) or oropharynx (about 60-70% of patient have HPV positive cancer).

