- Uncontrolled intercurrent illness including, but not limited to, ongoing or active infection, symptomatic congestive heart failure, uncontrolled hypertension, unstable angina pectoris, cardiac arrhythmia, active peptic ulcer disease or gastritis, active bleeding diatheses including any subject known to have evidence of acute or chronic hepatitis B, hepatitis C or human immunodeficiency

virus (HIV), or psychiatric illness/social situations that would limit compliance with study requirements or compromise the ability of the subject to give written informed consent

- Known history of active tuberculosis
- Receipt of live attenuated vaccination within 30 days prior to study entry or within 30 days of receiving durvalumab
- Female subjects who are pregnant, breast-feeding or male or female patients of reproductive potential who are not employing an effective method of birth control
- Patients with body weight < 30kg
- Any condition that, in the opinion of the investigator, would interfere with evaluation of study treatment or interpretation of patient safety or study results

Investigational Product(s), Dose and Mode of Administration:

Durvalumab, 750 mg Q2W (equivalent of 10 mg/kg Q2W) IV infusion x 2 administrations. In exceptional cases in which the window time to surgery is longer than 4 weeks, a third dose of Durvalumab of 750 mg IV infusion is allowed.

Study Assessments and Criteria for Evaluation:

Immune Response Assessments:

- a) Peripheral blood mononuclear cell interferon-γ production *in vitro* (ELISA) in response to commercially available peptide pools corresponding to HPV, p53, Mage-A3, Her2/neu, and survivin will be determined. Responses of patients whose tumor are HPV+ will be compared to those that are HPV-.
- b) PD-1+CD4+, PD 1+CD8+, PD-1L+, and Foxp3+CD4+ tumor-infiltrating cells will be quantified (0 to 3+) using standing immunofluorescence techniques.
- c) The following immune effector and regulatory responses will be assessed in blood using standard flow cytometric techniques: CD4+, CD8+, CD4+FoxP3+ Treg, and CD45RO+CD4+ memory T cells; CD3-CD56+ NK cells, and CD14-HLA-DR-CD15+ MDSC. The results of patients whose tumor are HPV+ will be compared to those that are HPV-.
- d) The relationship between levels of the miRs and the immune response to HPV, immune response to tumor associated antigens, and immune regulatory molecules/cells will be assessed.

Safety Assessments:

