- a) Clinical toxicity per NCI Common Terminology Criteria for Adverse Events version 4.0 and
- b) Any delays in planned surgery.

Efficacy Assessments:

Response to Durvalumab using CT scan and PET scan

Statistical Methods and Data Anlaysis:

For this pilot study our goal is to get preliminary descriptive data for a series of measures taken using blood, saliva and tumor tissue pre- and post- immunotherapy. With a sample size of 10 patients in each group (i.e. 10 with HPV+ and 10 HPV-) we will be able to estimate a 95% confidence interval for each group with confidence limits +/- 0.72 standard deviations. We can also examine the change in each measure (pre- versus post- therapy) to see whether any confidence intervals show a significant change from baseline (i.e., the measure increased (or decreased) by more than 0.72 standard deviations). This data would provide useful preliminary information concerning the potential mean value and variability for each measure of interest. It may also provide information about which possible measures are most impacted by the intervention within each group (HPV+/HPV-). Furthermore, if we were to compare groups, we would have 80% power to detect a difference in measures equal to 1.3 standard deviations of the measure of interest using a 2-sample t-test with alpha=0.05.

SCHEDULE OF STUDY ASSESSMENTS

Schedule of study assessments: Screening and Treatment Period

			All assessments	to be perfo	med pre-infusion	unless stated	otherwise	
Assessments to be performed at the times stipulated in the table and as clinically required in the management of the subject.	Pre-screening for PD-L1 status ONLY	Screening	Baseline First drug administration	Follow up	Second Drug Administration	Follow up	Before Surgery (3-17 days from last drug adm.)	Surgery
Day	-42 to -1	-28 to -1		Da	y 1 of the week (=	±3 days)		
Week	-6 to -1	-4 to -1	1	2	3	4		
Written informed consent/assignment of subject identification number	X							
Preliminary eligibility fulfilment (investigator's opinion)	Х							
Demography and history of tobacco and alcohol use		Х						
Previous treatments for SCCHN		Х						
HPV by PCR in FFPE	Xa							
Obtain archived or fresh tumour biopsy for PD-L1 assay, if applicable	X							
Formal verification of eligibility criteria		Х						
Medical and surgical history		Х						
Hepatitis A antibody Hepatitis B surface Ag, Hepatitis C antibody and HIV		Х						
Urine hCG or serum βhCG ^b		Х	As clinically indicated					

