5.1.2 Durvalumab Doses and treatment regimens

Durvalumab every 2 weeks x 2 administrations. A third dose will be allowed in the exceptional cases in which the window time to surgery is longer than 4 weeks. Surgery will follow 3-17 days after the last administration of Durvalumab.

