6.2 Dosage and Administration

Patients will receive Durvalumab 750 mg (equivalent of 10 mg/kg) every 2 weeks, two administrations. In exceptional cases of a longer than 17 days interval between the last administration of Durvalumab and surgery, a third dose of Durvalumab will be considered.

Dose Modification and Toxicity Management

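### Section 3.1 mandates a third durvalumab dose for surgery 15–17 days after dose 2, although dose 2 already meets the 3–17 day interval; separately, the infusion-time limits conflict (8 h against 4 h)

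*Combined protocol and SAP*

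**What the plan says.** **Interval to surgery.** Section 3.1 states: "An interval of 3 to 17 days must be ensured for all patients between the last administration of drug and surgery". The synopsis, the header of the pre-surgery column in the schedule of assessments, and Section 5.1.2 ("Surgery will follow 3-17 days after the last administration of Durvalumab") give the same range. Section 3.1 adds a narrower target: "A 7-14 days interval will be strongly considered and attempted in each case".

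**Third dose.** Four places govern it:

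- Section 3.1: in rare cases where surgery is "more than 2 weeks after second administration of Durvalumab, a third administration of drug must be given in order to ensure the proposed interval". The dose is mandatory.
- Section 6.2: for a "longer than 17 days interval between the last administration of Durvalumab and surgery, a third dose of Durvalumab will be considered". The dose is for consideration.
- Synopsis, dose and mode of administration: exceptionally, if the "window time to surgery is longer than 4 weeks, a third dose of Durvalumab of 750 mg IV infusion is allowed". The dose is optional.
- Section 5.1.2: the same 4-week condition as the synopsis, also optional.

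Neither the synopsis nor Section 5.1.2 says when the 4-week window starts. The schedule has no column for a third dose.

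**Infusion time.** Section 5.1.3, in its text and its table, allows up to 8 hours at room temperature including interruptions. Section 5.1.4 allows 4 hours from start to completion and otherwise requires a new preparation. For a reaction of Grade 2 or lower, Section 5.1.4 also permits a pause of up to 4 hours, followed by restarting at half the initial rate.

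**The concern.** The reason Section 3.1 gives for the extra dose is to secure the interval before surgery. On days 15 to 17 after dose 2 the only mandatory interval is already secured, so the rule requires a dose that its own purpose does not call for, and Section 6.2 does not trigger one. A clinician who doses at the usual two-week spacing for surgery on day 15 or 16 breaks the 3-day minimum; one who withholds breaks the mandatory wording.

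These patients are awaiting curative surgery. Section 1.5.3 asks for caution with even the second dose because surgery is near, and Section 3.3 lists delay or compromise of that surgery among the risks to avoid.

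The infusion conflict is a separate matter of drug handling. After a reaction and a long pause, whether staff finish or discard the same bag depends on which section they consult.

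**Working it through.** The plan gives no figure to reproduce here. The check compares the rules day by day, then does simple arithmetic on the infusion.

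**Third dose.** Let d be the days from dose 2 to surgery and g the days from dose 2 to dose 3. The rules are:

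- dose 2 alone complies if 3 ≤ d ≤ 17 (Section 3.1);
- Section 3.1 mandates dose 3 if d > 14;
- Section 6.2 considers dose 3 if d > 17;
- the interval from dose 3 to surgery is d − g.

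With two-weekly dosing, g = 14:

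| d | Dose 2 within 3–17? | Section 3.1 | Section 6.2 | d − 14 | Dose 3 within 3–17? |
|---|---|---|---|---|---|
| 14 | yes | no dose | no dose | – | – |
| 15 | yes | mandatory | no dose | 1 | no |
| 16 | yes | mandatory | no dose | 2 | no |
| 17 | yes | mandatory | no dose | 3 | yes |
| 18 | no | mandatory | consider | 4 | yes |
| 31 | no | mandatory | consider | 17 | yes |

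The triggers disagree on three calendar days: 15, 16 and 17. On two of them, a dose at 14-day spacing breaks the minimum.

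The breach depends on spacing. The schedule's ±3-day visit tolerance is not stated to cover a third dose. If it did, and dose 2 were on time with dose 3 three days early (g = 11), the intervals would be 15 − 11 = 4, 16 − 11 = 5 and 17 − 11 = 6 days. The minimum would then be met, but not the preferred 7–14 days.

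**The 4-week window.** Counted from dose 1 with dose 2 on day 14, four weeks is 28 days, and 28 − 14 = 14 days after dose 2. On that assumption the synopsis and Section 5.1.2 share the Section 3.1 threshold but keep an optional verb.

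**With a 17-day trigger.** Days 15–17 need no third dose. For d = 18 to 31, g = 14 gives 4 to 17 days, all compliant. At d = 18 the minimum requires g ≤ 18 − 3 = 15, so the timing of dose 3 still needs a rule.

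**Infusion.** The standard infusion is 60 minutes (Section 5.1.3). Suppose a reaction occurs at minute t (0 to 60), the pause lasts p minutes, and the rest runs at half rate and so takes 2(60 − t) minutes.

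Total = t + p + 2(60 − t) = 120 − t + p.

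- Full pause, p = 240: the total runs from 120 − 60 + 240 = 300 to 120 − 0 + 240 = 360 minutes, or 5 to 6 hours. This is over the 240-minute cap in Section 5.1.4 and under the 480 minutes in Section 5.1.3.
- To stay within 240 minutes: p ≤ 120 + t, so the longest usable pause is 2 to 3 hours, depending on when the reaction occurs.

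**The case against.** The strongest defence is that the interval Section 3.1 has in mind is the preferred 7–14 days, stated in the sentence just before. The 2-week trigger is the upper end of that range. The synopsis and Section 5.1.2 may share the threshold, and the 17 days in Section 6.2 could be read as the same rule plus the 3-day visit tolerance (14 + 3 = 17). That would explain how the texts arose, but it does not reconcile them. The 7–14 day range is only a target, Section 6.2 still uses another trigger and a weaker verb, and a dose at 14-day spacing leaves 1 to 3 days, further from the target than having no third dose.

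Other parts of the defence stand:

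- A reader might infer that the protocol forces a dose on a patient with toxicity. It does not. Section 4.3 (items 2 and 6) and Section 6.2.1 provide for stopping the drug. What is missing is explicit discretion to withhold because of upcoming surgery alone.
- A reader might infer that dosing 1 or 2 days before surgery is authorised. It is not. Sections 3.1 and 5.1.2 already require at least 3 days after the last dose. The fault is that two mandatory statements collide.
- Omitting dose 3 carries no stated penalty: Section 4.3 (item 12) and the efficacy analysis set in Section 11.1.2 require only two doses.
- A reader might infer bias in the biomarker results. The documents give no basis for deriving one.

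On infusion time, keeping to 4 hours satisfies both sections, and both require a new preparation once their limit is passed. That is a safe working rule, but it leaves the conflict between the pause and the cap inside Section 5.1.4.

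**Conclusion.** The point holds as a conflict between dosing instructions and is worth correcting. It covers surgery on three calendar days (15, 16 and 17 after dose 2), which is not a share of patients. Section 3.1 itself calls surgery beyond two weeks rare, so few of the 20 patients are likely to be affected. The breach of the 3-day minimum on days 15 and 16 assumes 14-day spacing between doses 2 and 3. No effect on an endpoint, on power or on a safety rate is shown or claimed.

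The infusion conflict is independent of this and twofold (8 hours against 4). A pause of the full permitted length always breaks the cap in Section 5.1.4, assuming a 60-minute infusion completed at half rate; shorter pauses may fit. Whether 8 hours is acceptable depends on stability data that the documents do not give.

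**What to change.** 1. In Section 3.1, change the trigger from more than 2 weeks to more than 17 days after the second dose, and replace the mandatory verb with a permissive one (may).
2. Use the same trigger and verb in the synopsis, Section 5.1.2 and Section 6.2, replacing the undefined 4-week window.
3. State with the trigger that a third dose is given only if surgery can still follow it by 3–17 days, preferably 7–14. The general interval rule already implies the outer limits; stating them here turns them into a timing instruction for dose 3.
4. Put one room-temperature infusion limit in Section 5.1.3 (text and table) and Section 5.1.4: 4 hours unless product stability data support 8. If 4 hours is kept, shorten the permitted pause in Section 5.1.4 or require a new bag whenever the total would exceed 4 hours.

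The cost is text edits in the synopsis and Sections 3.1, 5.1.2, 5.1.3, 5.1.4 and 6.2. No patients, visits or samples are added.
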